9.2 SAMPLE SIZE

Upon conclusion of the pilot, further recruitment to the study will occur with a planned interim analysis for futility and efficacy. Participants in the pilot study will continue to have their data analysed. The planned interim analysis is referred to as ‘stage 1’ analysis for convenience. The final analysis is referred to as ‘stage 2’ analysis. In each stage, there are three co-primary endpoints:

1. sensitivity (of the Avantect test),
2. specificity (of the Avantect test) and

3. resectability of diagnosed PCs

In the stage 1 interim analysis, these endpoints will be assessed within the intervention arm, as more information will be available on the diagnostic status of this group. In the stage 2 final analysis, the sensitivity and specificity of the test will be estimated within the intervention arm, whereas resectability will be compared between the arms.

The anticipated prevalence of a pancreatic cancer diagnosis within 3-years of follow-up within this population is 1%³. Conservative estimates place the anticipated sensitivity of the Avantect test at 65% sensitivity and 95% specificity in the detection of PC. Under usual care in the UK, 10-20%^{13,14} of pancreatic cancer patients receive surgery with curative intent due to the majority (80%) presenting at Stage III or Stage IV¹⁵. Data from the CAPS cohort¹⁶ in the US has demonstrated that it is possible to reduce the proportion of patients presenting with late stage disease if surveillance testing is conducted on at-risk subgroups, thus improving the availability of curative resection as a treatment strategy. It is hoped that the Avantect test can improve the resectability of pancreatic cancers from a rate of 14% in usual care to 40% in the intervention arm (just over a 2.5-fold increase).

With three co-primary endpoints, each endpoint must be reached for an overall successful result. To achieve an overall power of 90%, the power for each endpoint should be $90\%^{(1/3)} = 96.5\%$. Following guidance from Korevaar and colleagues¹⁷, the analysis will consist of a one-sided test at an cumulative alpha of 0.05 at the final analysis. Because there is an interim analysis at stage 1 for efficacy and futility, the one-sided significance level changes at the interim and final analysis.

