Two of the three co-primaries are metrics of test accuracy. In practice test results will not be available for all participants due to machine failure, insufficient blood sample quality, shipping or processing, or participants being unable to provide a blood sample. To reduce the number of participants where no test results are available, three collection time points are included. In the case where a blood draw did not occur or the sample was not analysable following a scheduled visit, a repeat blood draw will be arranged. The expected proportion of participants who are expected to not have a single Avantect result is 2.5%.

Using the PropTestPower function in the R package EnvStats, it was determined that 73 individuals with pancreatic cancer are required in each arm to detect a change of resectability from 14% in usual care to 40% in the intervention arm. At the stage 2 final analysis, allowing for interim analysis, the overall power would be 96.5%. Allowing for 2.5% loss to arrive at the Per Protocol population (see section 9.4), this increases to 75 cases per arm (150 total), which at an event rate of 1% leads to a recruitment target of 7,500 per arm (15,000 total). As only samples from the intervention arm are to

be tested for the purpose of the analysis, with an anticipated test sensitivity of 65% and specificity of 95%, this leads to the following confusion matrix in the intervention per protocol group (7,312):

		Diagnostic status	
		Has PC diagnosis	Does not have PC diagnosis
Avantect test result	Detected	48	362
	Not detected	25	6,877

With 73 cases of pancreatic cancer of which $48/73 = 65\%$ were detected by the Avantect test, this would be sufficient to rule out a sensitivity lower than 42 % in the stage 2 final analysis at 96.5% power. On discussion with the FDA, a specificity of 92% would be considered acceptable within this clinical context. With 6,877 individuals without a pancreatic cancer diagnosis of which $6,877/7,239 = 95\%$ are expected to be detected by the Avantect test, more than 99% power is achieved to rule out a specificity lower than 92%.

Definition of ‘promising result’ in study stage 1 to guide progression to study stage 2

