9.4 STATISTICAL ANALYSIS PLAN (SAP)

This study will be analysed using the principles of the International Conference on Harmonisation E9 guidelines and reported according to the CONSORT guidelines. A full and detailed statistical analysis plan will be developed prior to the final analysis of the study. The main features of which are described here.

All analyses will be conducted on a Per Protocol population. All individuals in the control arm will qualify for the Per Protocol population. Individuals in the intervention arm will qualify for the Per Protocol population if they have at least one analysable Avantect test result (i.e. either “Detected” or “Not detected”). Per Protocol population will be analysed according to the original randomisation

group even when other aspects of the protocol are not followed e.g.unplanned cross-over, study withdrawal. It is expected that 98.8% of the randomised population will qualify for the Per Protocol population.

The co-primary outcomes are Avantect sensitivity and specificity in detecting PC, and resectability rate. Sensitivity is defined as the proportion of participants in the intervention arm with one (or more) Avantect “detected” test results who have pancreatic cancer diagnosed via imaging in relation to all individuals in the intervention arm who had pancreatic cancer diagnosed. Specificity is defined as the proportion of participants in the intervention arm with one or more Avantect “not detected” test results, and no Avantect “detected” results, who did not have a pancreatic cancer diagnosis in relation to all individuals in the intervention arm who did not have a pancreatic cancer diagnosis. Resectability is defined as the proportion of PCs deemed resectable by the study MDT divided by the number of PCs and will be compared between arms. For all co-primary endpoints, a logistic model will be used to estimate uncertainty. At the stage 1 interim analysis, due to alpha spending to reach a cumulative total alpha of 0.025 for each co-primary endpoint, a one-sided 98.6% confidence interval will be calculated to estimate the lower-bound of the observed proportion. At the stage 2 final analysis, a one-sided 98.5 % one-sided interval will be calculated instead. Co-primary endpoints will also be assessed for regular oversight meetings, where a one-sided 95% confidence interval will be used.

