At the stage 1 interim analysis, co-primaries will be considered ‘futile’, ‘promising’ or ‘efficacious’ according to the following table:

	Expected proportion	Futility threshold at stage 1	Promising result range at stage 1	Efficacy threshold at stage 1
Sensitivity	65%	<46.5%	46.5% to 63.1%	>63.1%
Specificity	95%	<92.0%	92.0% to 94.9%	>94.9%
Resectability	40%	<21.0%	21.0% to 38.1%	>38.1%

At the stage 2 final analysis, the sensitivity co-primary will be considered successful if a sensitivity of 49% can be ruled out with a one-sided p-value of 0.03 among participants in the intervention arm. Specificity will be considered successful if a specificity of 92% can be ruled out with a one-sided p-value of 0.03 among participants in the intervention arm. Resectability will be considered successful if the resectability rate in the intervention arm is higher than the rate in the control arm at a one-sided p-value of 0.03.

Secondary outcomes, in order of importance, are defined as follows, which all are calculated with a minimum of 90% power:

Stage shift - The analysis will be conducted by comparing the proportion of PC cases diagnosed at stage I/II vs III/IV between the intervention and control arms. A proportion of 60% (44/73 PCs) is expected in the intervention arm versus 35% (26/73 PCs) in the control arm, which provides 90% power at a one-sided alpha of 0.05. Stage shift will be considered successful if the proportion in the intervention arm is higher than the rate in the control arm at a one-sided p-value of 0.05.

PPV in detecting PC - The analysis will be conducted within the intervention arm. With a sample size of 7,500, PC prevalence of 1%, and 2.5% lost from the per protocol population, there will be an expected 410 individuals with an Avantect “detected - abnormal” result. 11.6% (48/410) are expected to have a PC. PPV will be considered successful if a null PPV of 5% can be ruled out at a one-sided p-value of 0.05.

NPV in ruling out PC - The analysis will be conducted within the intervention arm with a sample size of 7,500, PC prevalence of 1%, and 2.5% lost from the per protocol population, will be an expected 6,902 individuals without an Avantect “detected - abnormal” result. 99.6% (6,877/6,902) are expected to not have a diagnosis of PC. NPV will be considered successful if a null NPV of 99% can be ruled out at a one-sided p-value of 0.05.

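### The final success rule for sensitivity uses a 49% null, but the stated 96.5% power belongs to a 42% null; if 49% governs, power is about 77–83% at one-sided 0.03

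*Protocol*

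**What the plan says.** Section 9.2 describes three co-primary endpoints, all of which must be met: "To achieve an overall power of 90%, the power for each endpoint should be" 96.5%, the cube root of 90%. The number of cancers, 73 per arm, is derived from the resectability comparison of 14% against 40%. Section 9.2 then asks what those 73 intervention-arm cancers can show about sensitivity at an expected 65%, and answers that "this would be sufficient to rule out a sensitivity lower than 42 % in the stage 2 final analysis at 96.5% power".

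Section 9.4 defines success at that same final analysis differently: "the sensitivity co-primary will be considered successful if a sensitivity of 49% can be ruled out with a one-sided p-value of 0.03".

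For specificity, both sections use 92%. Only the sensitivity null differs.

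The error rate attached to these tests also varies. In section 9.2, "the analysis will consist of a one-sided test at an cumulative alpha of 0.05 at the final analysis". In section 9.4, the intervals are set "due to alpha spending to reach a cumulative total alpha of 0.025 for each co-primary endpoint", which gives a one-sided 98.5% interval at the final analysis, whereas the success rules further down in the same section use a one-sided p-value of 0.03.

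**The concern.** A power statement is only meaningful for the hypothesis actually tested. Section 9.2 gives 96.5% for excluding 42%, while section 9.4 requires the trial to exclude 49%. The second hurdle is seven percentage points higher, with the same number of cancers and the same expected sensitivity, so the same power cannot apply to both.

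Two things are at stake. The 90% overall power rests on each co-primary having 96.5%, so a shortfall in one removes it. There is also a band of final results that would exclude one figure and not the other, so the protocol should state a single null for a co-primary endpoint before any outcome data are examined.

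**Working it through.** **Inputs.** From section 9.2: n = 73 cancers in the intervention arm; true sensitivity p1 = 0.65; null p0 = 0.42; target power 96.5%; specificity power above 99%; interim information 43.8%. From section 9.4: null p0 = 0.49; one-sided 0.03; final interval one-sided 98.5% (alpha 0.015); a logistic model for uncertainty.

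**Methods.** One-sample, one-sided test.
- Normal approximation: critical proportion c = p0 + z·√(p0(1−p0)/n); power = Φ[(p1 − c)/√(p1(1−p1)/n)], where √(0.65·0.35/73) = 0.0558.
- Exact binomial: smallest k with P(X ≥ k | p0) ≤ alpha; power = P(X ≥ k | 0.65).
- Logit-Wald: smallest k whose lower bound on the logit scale exceeds p0. This is the closest match to the logistic model in section 9.4.

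**Step 1: reproduce the stated 96.5% (null 42%).**
- Alpha 0.03: c = 0.42 + 1.881·0.0578 = 0.529; power Φ(2.17) = 98.5%. Exact: at least 40/73, 97.3%.
- Alpha 0.015: c = 0.42 + 2.170·0.0578 = 0.545; power Φ(1.87) = 97.0%. Exact: at least 41/73, 95.4%.

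The stated figure is reproduced to within two points. By normal approximation, the null that 73 cases exclude with exactly 96.5% power is 42.3% at alpha 0.015 and 44.0% at 0.03.

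**Step 2: the success rule as written (null 49%).**

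| One-sided alpha | Exact | Normal | Logit-Wald |
|---|---|---|---|
| 0.03 | 76.7% (≥45/73) | 81.5% | 83.4% (≥44/73) |
| 0.015 | 68.7% (≥46/73) | 72.3% | 68.7% (≥46/73) |
| 0.05 | 83.4% (≥44/73) | 87.3% | 88.7% (≥43/73) |

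For the normal result at 0.03: c = 0.49 + 1.881·0.0585 = 0.600; (0.65 − 0.600)/0.0558 = 0.895; Φ(0.895) = 81.5%. The logit-Wald rule at 0.03 gains power partly because its true size is 3.5%, above the nominal 3%. A plain Wald test gives 83.8% at 0.03 and 75.7% at 0.015.

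**Step 3: count interim efficacy as success.** Take 31–32 interim cancers (43.8% of 73 = 32) and the 63.1% efficacy bound, followed by the final rule of at least 44 or 45 of 73. Power is then about 81–86%.

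**Step 4: overall power.** Use 96.5% for resectability and 99% for specificity, and multiply as the protocol's cube root does.
- Exact at 0.03: 0.767 × 0.965 × 0.99 = 73%.
- Logit-Wald at 0.03: 0.834 × 0.965 × 0.99 = 80%.
- Alpha 0.015: 0.687 to 0.723 × 0.965 × 0.99 = 66–69%.

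**Step 5: results on which the two nulls disagree.** By exact test at 0.03, 40/73 excludes 42% but 45/73 is needed to exclude 49%. Results of 40 to 44 detected (54.8–60.3%) fall between the two. If true sensitivity is 65%, this happens with probability 0.973 − 0.767 = 21%.

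**The case against.** The strongest reply is that 42% may be the intended null and 49% a drafting slip. The stated power would then be sound. The protocol does not settle this, so the shortfall has to be stated as conditional on 49%. The contradiction itself remains either way.

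Some stronger readings are tempting but not supported:

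- *The trial was sized on a 42% null.* It was not. The 73 cancers per arm come from resectability; 42% is only what section 9.2 says those cancers can exclude.
- *The power is a single, narrow figure.* It depends on the method, on whether 0.03 or the 98.5% interval applies, and on whether an interim crossing counts as success.
- *Overall power is firmly 73–80%.* The product assumes independence. Sensitivity and resectability are measured on the same intervention-arm cancers, and a positive association is plausible. The product would then understate overall power, although overall power cannot exceed that of sensitivity alone.
- *The Stage 1 thresholds show which null was used, or are themselves errors.* A futility bound (46.5%) below the null is not wrong in itself at 43.8% information. The 63.1% efficacy bound reproduces cleanly from neither null: with 32 cancers and alpha 0.014, the critical value is about 61% for 42% and 68% for 49%. The figure of 32 also applies a three-year 1% rate to about one year of follow-up.
- *The trial has two competing success rules.* Only section 9.4 states a final success rule; section 9.2 makes a power statement. The rule is the stricter of the two, so as written the discrepancy costs power and does not make a false success easier.

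**Conclusion.** The two sections give different nulls for the same co-primary test, and the protocol's power statement holds for only one of them. If 49% governs, with 73 cancers and a true sensitivity of 65%, power at one-sided 0.03 is about 77% (exact) to 83% (logit-Wald). It is about 69–72% with the 98.5% interval, and about 81–86% if interim efficacy counts. No variant examined reaches 96.5%. Overall power at 0.03 is then roughly 73–80% under independence, not 90%. If 42% governs, the stated power stands and the success rule in section 9.4 is wrong. The documents do not show which was meant. Because this concerns the success criterion of a co-primary endpoint, it must be corrected.

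**What to change.** Before Stage 1, choose one sensitivity null and use it in both section 9.2 and section 9.4. Settle the one-sided alpha at the same time: cumulative 0.05 or 0.025, and 0.03 or the 98.5% interval at the final analysis.

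- If 42% is intended, change the success rule in section 9.4.
- If 49% is intended, restate the sensitivity and overall power in section 9.2, naming the test method and whether an interim crossing counts as success. Re-derive the Stage 1 sensitivity thresholds (46.5% and 63.1%) from the chosen null and alpha, and state the number of interim cancers assumed.

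The cost is protocol wording and some recalculated figures. No extra participants are needed to correct the text; if 49% is kept, the stated power becomes less favourable. Keeping both 49% and 96.5% power at one-sided 0.03 would be a different decision, requiring about 128 intervention-arm cancers (normal approximation) instead of 73.

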Resection rate of PC. The analysis will be conducted by comparing resection between the intervention and control arms. With a sample size of 15,000, PC prevalence of 1%, and 2.5% lost to follow-up, there will be an expected 73 cases of PC in each arm. It is assumed that 5% of those deemed resectable will not undergo resection, for an expected rate of 38% (28/73) in the Intervention arm versus 13% (9/73) in the control arm. Resection rate will be considered successful if the proportion in the intervention arm is higher than the rate in the control arm at a one-sided p-value of 0.05.

For analyses of exploratory outcomes, the following applies:

Time-to-event outcomes (time to PC diagnosis and overall survival) will be analysed using a Cox regression model to determine the hazard ratio (and 95% confidence interval) between groups. This will be supported by a Kaplan-Meier plot for each group, median survival (and 95% confidence intervals), and estimates of 3-year survival (T0-T3) (alongside the difference in proportions and corresponding 95% confidence interval). The 6-item STAI will be analysed using a t-test or non-parametric suitable alternative if data are not normally distributed. Performance characteristics for high-grade neoplasia include sensitivity, specificity, PPV and NPV. They will be analysed as described

SAFE-D Clinical Performance Study Protocol Version 4, IRAS Ref: 326332 31-JUL-2025 Page 49 of 68

above, when high-grade neoplasia is also considered as Disease Positive, and when high-grade neoplasia alone (with the exclusion of pancreatic cancer) is considered as Disease Positive. Two-sided p-values will be presented for exploratory outcomes.

Unless otherwise stated, continuous data will be presented as means and standard deviations and analysed using a linear regression modelling framework. If data are skewed, medians and ranges will be presented. To analyse skewed data we will attempt to find a suitable transformation to allow a linear modelling approach. If this is not possible, we will explore whether another suitable parametric distribution fits the data. If not, a non-parametric approach, such as quantile regression, will be used. Binary data will be reported in terms of odds ratios and analysed using logistic regression modelling, unless otherwise stated.

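### Each of the four secondary endpoints can be called successful at its own one-sided 0.05, whatever happens to the co-primaries or to higher-ranked secondaries

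*Protocol*

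**What the plan says.** Protocol section 9.4 opens the list with "Secondary outcomes, in order of importance, are defined as follows, which all are calculated with a minimum of 90% power". The order is stage shift, PPV, NPV, resection, the same as in sections 2.3 and 2.4. Each endpoint then has its own criterion:

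- Stage shift: "Stage shift will be considered successful if the proportion in the intervention arm is higher than the rate in the control arm at a one-sided" (level 0.05).
- PPV: "PPV will be considered successful if a null PPV of 5% can be ruled out at a one-sided p-value of 0.05".
- NPV: "NPV will be considered successful if a null NPV of 99% can be ruled out at a one-sided p-value of 0.05".
- Resection: "Resection rate will be considered successful if the proportion in the intervention arm is higher than the rate in the control arm at a one-sided" (level 0.05).

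None of the four refers to another secondary or to a co-primary. Section 9.2 requires all three co-primaries for the trial to succeed overall, but does not make that a condition for testing the secondaries. The protocol contains no hierarchy, alpha split or other multiplicity rule for the secondary family. Section 9.4 leaves full detail to a later SAP and presents its own text as the main features.

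**The concern.** The secondaries are powered endpoints with pass/fail rules, so each can produce a formal claim. With four such rules and nothing linking them, the chance that at least one passes wrongly exceeds the level of any single test.

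The case that matters most is a test that classifies well but does not change what happens to patients. Resectability, a co-primary, would then be expected to fail. Resection is nearly the same quantity: section 9.4 derives its expected rates by assuming that 5% of resectable cases are not resected (40% × 0.95 = 38%; 14% × 0.95 = 13.3%). Stage shift addresses the same question of earlier detection. As written, either could still be labelled successful after resectability had failed.

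**Working it through.** **Inputs from the protocol (sections 9.2 and 9.4).** Four tests at one-sided 0.05 (critical z = 1.645); 73 pancreatic cancers per arm; stage shift 60% v 35%; resection 28/73 v 9/73; PPV 48/410 against a null of 5%; NPV 6,877/6,902 against a null of 99%; 7,312 in the intervention per-protocol group; prevalence 1%; overall co-primary power 90%.

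**Assumption.** The correlation ρ between the stage-shift and resection statistics is not given, so it is varied from 0 to 0.9. PPV or NPV is taken as independent of the arm comparisons.

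**1. The plan's own figure.** Stage-shift power, normal approximation:

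- Null SE = √(2 × 0.475 × 0.525 / 73) = 0.0827
- Alternative SE = √((0.60 × 0.40 + 0.35 × 0.65) / 73) = 0.0800
- Power = Φ((0.25 − 1.645 × 0.0827) / 0.0800) = Φ(1.425) = 92.3%

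Using 44/73 v 26/73 gives 91.6%; with a continuity correction at 60% v 35% it is 89.5%; Fisher's exact test gives 90.7%. The stated 90% reproduces. The same methods give 98.1% for resection, 99.9% for PPV and above 99.9% for NPV.

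**2. Only the two arm comparisons null.** P(at least one false success) = 1 − Φ₂(1.645, 1.645; ρ), where Φ₂ is the bivariate normal distribution function.

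**3. One of PPV or NPV also at its null.** P = 1 − 0.95 × Φ₂(1.645, 1.645; ρ).

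| ρ | Two nulls | Three nulls |
|---|---|---|
| 0 | 9.75% | 14.3% |
| 0.5 | 8.8% | 13.3% |
| 0.9 | 6.8% | 11.5% |

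**4. Can all four be at their nulls?** Four independent tests would give 1 − 0.95⁴ = 18.5%. The protocol's figures rule this out. Keep 410 detected and 6,902 not detected, with 73 cancers:

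- PPV = 5% means 0.05 × 410 = 20.5 cancers detected and 52.5 missed. NPV = 1 − 52.5/6,902 = 99.24%, so the NPV null is false.
- NPV = 99% means 0.01 × 6,902 = 69 missed and 4 detected. PPV = 4/410, about 1%, which is so far below 5% that a false PPV claim is practically impossible.
- Both sit at their boundary only with 20.5 + 69.0 = 89.5 cancers, a prevalence of 89.5/7,312 = 1.22%.

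At 1% prevalence, then, no more than three of the tests contribute materially to the error.

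**5. Power under a gated fixed sequence.** Once the gate is open, and treating the tests as independent, the power to pass all four is 0.923 × 0.999 × 1.000 × 0.981 = 0.90. Behind the 90% co-primary gate, stage shift has 0.90 × 0.923 = 83% and resection, last in line, 0.90 × 0.923 × 0.999 × 1.000 × 0.981 = 81%.

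**6. Bonferroni for comparison.** At 0.0125 each, stage-shift power is 79.1% and resection 92.5%. Stage shift would miss the stated 90% minimum.

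**The case against.** The strongest reply is that multiplicity among secondaries is commonly left to the SAP, which is not shown. A ranking by importance with full alpha for each test is also just what a fixed sequence needs, so the SAP could add one. It could. But section 9.4 already states four complete and unconditional success rules, and a SAP that imposed a gate would be changing them. The point is what the protocol fixes, not what it omits.

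A reader might also infer stronger things that the protocol does not support:

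- **That the error is 14 to 18%, or 18.5%.** The upper figures need all four nulls at their boundaries, which the 1% prevalence excludes. In the scenario described above, where the test classifies well, PPV and NPV claims would be true and only the two arm comparisons could be false.
- **That the trial as a whole could be declared a success on a secondary.** Section 9.2 reserves that for all three co-primaries. Section 9.4 labels individual endpoints only.
- **That a stated 5% family-wise rate is breached.** The 0.05 is per test, and no family-wise rate is claimed.
- **That 0.05 is looser than the 0.03 used for the co-primaries.** The 0.03 is the final-look share of the cumulative one-sided 0.05 in section 9.2, whereas no interim test is stated for the secondaries. (Section 9.4 elsewhere gives a cumulative 0.025; that is a separate inconsistency.)

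The objection that a gate lowers the unconditional power is correct, and is counted as a cost below.

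**Conclusion.** The point holds in limited form. The four rules are unconditional, the ranking is not used, and the chance of at least one false secondary success exceeds the per-test 5%: about 7 to 10% with only stage shift and resection null, and about 11.5 to 14.3% with PPV or NPV also at its null. These figures rest on the assumed correlation of 0.9 to 0, on independence of PPV or NPV from the arm comparisons, and on the nulls being true. The primary conclusion is untouched. What is uncontrolled is any formal secondary claim, above all a resection or stage-shift success after resectability has failed.

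**What to change.** State in section 9.4, and carry into the SAP, that the secondaries are formally tested only if all three co-primaries succeed. They are then tested in the listed order (stage shift, PPV, NPV, resection), each at one-sided 0.05, stopping at the first non-significant result. Anything not reached is reported as an estimate with an interval and no success label. This uses the sponsor's own ranking and holds the secondary family-wise error at or below 0.05, without splitting alpha.

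Alternatively, describe all four as supportive and remove the success label.

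The cost is a short text change and no extra participants. Under the sequence there is no formal secondary claim after a co-primary or an earlier secondary fails. The 90% power statement must also be reworded as per test and conditional on reaching that test, because unconditional power is roughly 81 to 83% for resection and stage shift under independence. Positive dependence between resectability and these two endpoints would raise those figures.
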